Single agent immune checkpoint inhibitor treatment, including therapies blocking PD-L1/PD-1 as well as CTLA-4 mediated signaling, have demonstrated that durable anti-tumor responses can be achieved in mCRPC. Immune checkpoint inhibitors including ipilimumab and pembrolizumab have led to durable tumor responses in a limited number of cases in mCRPC, but increasing the proportion of patients who respond to single agent checkpoint blockade has been challenging. [name] at UCSF led the first in human study of ipilimumab in mCRPC. Overall, the tumor immunogenicity, as reflected by mutational burden, tumor infiltrating lymphocytes, and tumor PD-L1 expression, are low in prostate tumors relative to other tumor types such as melanoma. In the KEYNOTE-028 study of pembrolizumab in mCRPC patients, the tissue screen positivity rate for PD-L1 expression in archival tumor tissue was less than 10%, and even in PD-L1 positive tumors, the objective response rate by RECIST 1.1 criteria was only 17%. However, in those patients who experienced a tumor response, there was durable regression of disease with median duration of response of over 15 months. For the majority of mCRPC patients who do not benefit from single agent immune checkpoint inhibitors, there is an unmet medical need to enhance tumor immunogenicity with priming therapy to enhance TILs, induce PD-L1 expression, and expand the T cell repertoire, thereby translating into a significant improvement in proportion of patients achieving durable tumor response.

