2.1 Objectives

Primary Objectives

Part A: To determine the recommended phase 2 dose and schedule of ¹⁷⁷Lu-PSMA-617 in combination with pembrolizumab in patients with mCRPC.

Part B (Dose Expansion): To determine the objective response rate by RECIST 1.1 criteria.

Secondary Objectives

1. To characterize the safety profile of the combination.
2. To determine the median duration of response by RECIST 1.1 criteria.
3. To determine the proportion of patients who experience $\geq 50\%$ decline from baseline in serum PSA.
4. To determine the median PSA progression-free survival.
5. To determine the median time to symptomatic skeletal related event.
6. To determine the 6 month radiographic progression-free survival rate and median radiographic progression-free survival.
7. To determine the median overall survival.

Correlative Objectives

1. To assess the lesion-specific response rate by baseline PSMA avidity on ⁶⁸Ga-PSMA-11 PET.
2. To quantify the change from baseline in T cell repertoire, circulating T cell subsets, tumor infiltrating lymphocytes, and tumor PD-L1 expression by immunohistochemistry after one priming dose of Lu-PSMA RLT.
3. To explore the relationship between timing of the ¹⁷⁷Lu-PSMA-617 priming dose with initiation of pembrolizumab with respect to immunologic, safety, and efficacy outcomes.
4. To descriptively characterize the patterns of uptake on ⁶⁸Ga-PSMA-11 PET at the time of disease progression.
5. To explore relationship between tumor genomic profile with clinical outcomes including response rate and progression-free survival.
6. To explore the relationship between tumor dosimetry with objective response.

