⁷ Tumor biopsy will be performed during Screening and within 7 days preceding C2D1 visit. Screening biopsy must be performed prior to initiation of study treatment but is not subject to 28-day screening window. Bone biopsies are acceptable if no soft tissue lesion is amenable for biopsy. The same lesion should be selected for the follow up biopsy whenever feasible.

⁸ Whole blood (40 mL in Na-Heparin green top tube) will be collected on C1D1 (pre-dose), C2D1 (pre-dose), C3D1 (pre-dose), on Day 1 of every 3 cycles thereafter (e.g. C6D1, C9D1, etc), and at the time of disease progression

⁹ SPECT/CT dosimetry scan is optional.

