8.4.3 Analytic Plan for Correlative Endpoints

Lesion-specific response rate by baseline PSMA avidity on ⁶⁸Ga-PSMA-11 PET:

All target lesions on baseline cross-sectional imaging will be assessed for response (e.g. > 30% reduction in longest diameter) on subsequent imaging during the course of study. The median baseline uptake on Ga-PSMA-11 PET between responding versus non-responding lesions will be compared using Mann-Whitney test. In addition, Spearman's rank correlation will be used to compare baseline lesion uptake on Ga-PSMA-11 PET with percent change from baseline in longest tumor diameter on subsequent cross-sectional imaging on study.

Percent change from baseline in T cell repertoire, circulating T cell subsets, tumor infiltrating lymphocytes, and tumor PD-L1 expression by immunohistochemistry after one priming dose of Lu-PSMA RLT:

T cell repertoire will be estimated using Morasita's distance as previously described. Quantification of circulating T cell subsets and TILs will be performed using flow cytometry and immunohistochemical analysis of tumor tissue and whole blood, respectively. PD-L1 expression will be analyzed as the percentage of tumor cells with positive surface expression. Correlative testing may be performed at outside laboratory facilities (i.e. Strata Oncology). The percent change from baseline in these parameters will be reported using descriptive statistics (e.g. median, range, standard deviation). In an exploratory fashion, the study cohort will be dichotomized by those with percent change from baseline above and below median and efficacy outcomes will be compared between dichotomized subgroups using log-rank test for time-to-event endpoints (e.g. rPFS, duration of response) and Fisher's exact test for categorical variables (e.g. objective response rate, 6-month rPFS rate, PSA50 response rate).

Genomic Sequencing

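### Percent change from baseline (Section 8.4.3) has no value when baseline PD-L1 is 0%, and no baseline to divide by for a repertoire distance in Schedules 1 and 2

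*Combined protocol and SAP*

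**What the plan says.** Correlative Objective 2 (Section 2.1) is "To quantify the change from baseline in T cell repertoire, circulating T cell subsets, tumor infiltrating lymphocytes, and tumor PD-L1 expression" after one priming dose. It asks for change and does not require a ratio.

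Section 8.4.3 turns this into percent change for all four parameters: "The percent change from baseline in these parameters will be reported using descriptive statistics", with median, range and standard deviation as examples. On the scales, it says "PD-L1 expression will be analyzed as the percentage of tumor cells with positive surface expression" and "T cell repertoire will be estimated using Morasita's distance as previously described". For the exploratory link to outcome, the cohort is "dichotomized by those with percent change from baseline above and below median". The two groups are then compared by log-rank test for time-to-event endpoints and by Fisher's exact test for categorical ones. The section gives no rule for a zero baseline, plans no absolute change or conversion count, and names no baseline value for the distance.

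Section 1.4 describes the need for "priming therapy to enhance TILs, induce PD-L1 expression, and expand the T cell repertoire". It also reports, from an earlier pembrolizumab study in mCRPC, that "the tissue screen positivity rate for PD-L1 expression in archival tumor tissue was less than 10" percent.

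**The concern.** Percent change divides by the baseline value. A PD-L1 score can be 0%, and the protocol's own background suggests that low or zero scores will be common. The patient who shows induction most clearly, from no positive cells to some, is then the one for whom the planned measure has no result. A patient who stays at 0% has none either. Whether a patient enters the PD-L1 summary and the median split therefore depends on the baseline being above zero, not on what treatment did.

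Baselines just above zero cause a second problem. They stay in the summary with very large percentages, which can dominate the range and standard deviation.

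For repertoire the difficulty is structural. A distance compares two samples, so one baseline sample does not supply a baseline distance to divide by.

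The paired biopsies matter to this trial. Section 1.7.1 gives them as one reason for raising the expansion cohort from 12 to 25 patients, in the hope of identifying likely responders, and the median split is one of the analyses meant to link them to outcome.

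**Working it through.** The plan gives no figure of its own for this analysis. The archival positivity rate is cited from another study and cannot be re-derived.

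**Inputs from the documents.** Planned patients: 18 in Part A + 25 in Part B = 43 (Section 3.1). PD-L1 scale: 0 to 100% of tumor cells (Section 8.4.3). Archival positivity: below 10% (Section 1.4). Blood draws: Sections 5.2 to 5.4.

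**Assumptions not in the documents.** All 43 patients have an evaluable biopsy pair. Baseline positivity is 10%, with 5% as a check because the cited rate is an upper bound. The share *s* of screen-negative tumors scoring exactly 0% is 50% to 100%.

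**1. The measure at the level of one patient.** Percent change = 100 × (follow-up − baseline) / baseline.

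| Baseline → follow-up | Percentage points | Percent change |
|---|---|---|
| 0% → 0% | 0 | undefined (0/0) |
| 0% → 5% | +5 | undefined |
| 0% → 50% | +50 | undefined |
| 1% → 5% | +4 | +400% |
| 1% → 50% | +49 | +4900% |
| 10% → 50% | +40 | +400% |

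**2. How many patients have no value.** P(baseline 0) = (1 − positivity) × *s*. The expected number is 43 times this, and the last column is a binomial tail.

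| Positivity | *s* | P(baseline 0) | Expected with no value, of 43 | P(more than half have none) |
|---|---|---|---|---|
| 10% | 50% | 0.450 | 19.4 | 0.25 |
| 10% | 75% | 0.675 | 29.0 | 0.99 |
| 10% | 100% | 0.900 | 38.7 | > 0.999 |
| 5% | 50% | 0.475 | 20.4 | 0.37 |
| 5% | 75% | 0.7125 | 30.6 | 0.998 |
| 5% | 100% | 0.950 | 40.9 | > 0.999 |

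For Part B alone at 10% positivity, the range is 25 × 0.450 = 11.25 to 25 × 0.900 = 22.5 patients. At 10% positivity, more than half are expected to have no value once *s* exceeds 0.5 / 0.9 = 56%.

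**3. Repertoire.** A Morisita-type distance of a sample from itself is 0. In the Morisita-Horn form, 1 − 2Σx² / (Σx² + Σx²) = 0. Dividing by that has no meaning, and the baseline-to-follow-up distance is already the change. A non-zero baseline distance would need two pre-treatment samples. In Schedule 1, blood "will be collected on C1D1 (pre-dose), C2D1 (pre-dose), C3D1 (pre-dose") and then at later cycles, so only one draw precedes treatment. Schedule 2 has the same draws. Schedule 3 has two draws before the radioligand (C1D-21 and C1D1), but the first pembrolizumab dose falls between them and the plan does not name that pair as a baseline.

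**4. Would a median split on absolute change work for PD-L1?** Take 10% positivity, all negatives at 0%, and 20% to 30% of negatives converting (illustrative rates, not in the documents). Then 38.7 × 0.8 = 31.0 down to 38.7 × 0.7 = 27.1 of 43 patients go from 0% to 0% and have a change of exactly 0. That is more than half, so the median is 0 and those patients fall neither above nor below it. Changing the scale alone does not rescue the split. With a smaller *s* there are fewer ties.

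**The case against.** The strongest reply concerns extent. A reader might infer that PD-L1 percent change is lost for nearly everyone. The documents do not support that: screen-negative is not the same as 0%, no cut-off is stated, the cited rate comes from archival tissue in another study, and this trial uses a screening biopsy. A near-zero baseline is computable, though unstable. With half of negatives at exactly 0%, most patients would still have a value. This stands, and it is why the size is given as a range.

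Second, the raw scores are still collected, so an analyst could compute absolute change later or rank any rise from 0% as above the median. That is also true: the data are not destroyed. But no such rule is prespecified, a patient staying at 0% still has no percent change, and a choice made after seeing the data can alter who falls on which side of the median.

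Third, the repertoire wording may be a loose blanket phrase, and the method is cited as already described in a source the documents do not reproduce. An analyst may well use the distance directly. That would be sensible, but Section 8.4.3 says otherwise.

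Three further inferences are tempting and unsupported. The loss should not be stated as lost power: no test of the immune change itself is planned and no conversion rate is given. No zero-baseline problem is shown for circulating T cell subsets or tumor infiltrating lymphocytes. Nor can it be said that the flaw distorts the choice of schedule: Section 3.1 mentions immunologic effects, but nothing says the percent-change summary is the input, and Section 8.4.1 names only safety and efficacy data.

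**Conclusion.** The concern holds for two of the four parameters. For PD-L1, the rule as written gives no value at a 0% baseline, so a conversion from 0% is left out of both the summary and the median split. Assuming 43 biopsy pairs and 10% positivity, about 19, 29 or 39 patients would be affected if 50%, 75% or 100% of negatives score exactly 0%. Which of these applies cannot be settled from the documents. For repertoire, percent change of a distance has no usable denominator in Schedules 1 and 2, and no named one in Schedule 3.

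This is a stated rule that fails when followed, so it should be corrected. Its reach is limited to exploratory correlatives; the primary and secondary endpoints are unaffected.

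**What to change.** Amend Section 8.4.3 as follows.

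- **PD-L1:** report absolute change in percentage points, and the number of patients converting from negative to positive and the reverse. State the cut-off for positive. For the log-rank and Fisher comparisons, group patients by conversion or by any increase (yes/no) instead of a median split, which could tie at 0.
- **T cell repertoire:** report the baseline-to-follow-up distance itself, with no division by baseline, and name the baseline sample for each schedule.
- **Circulating T cell subsets and tumor infiltrating lymphocytes:** leave on percent change unless zero baselines occur.

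The cost is a wording change, with the same samples and assays. The downside is that the four parameters no longer share one percent scale.

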3.1 Characteristics

This is a single-center Phase 1b open-label, study of PSMA-targeted radionuclide therapy with ¹⁷⁷Lu-PSMA-617 in combination with pembrolizumab in patients with mCRPC who have previously progressed on at least one prior androgen pathway inhibitor (e.g. abiraterone, enzalutamide, apalutamide). Patients must have at least three metastatic lesions which are PSMA-avid on baseline ⁶⁸Ga-PSMA-11 PET imaging.

In **Part A** of the study, patients will be enrolled in sequential fashion to one of treatment schedules with respect to timing of ¹⁷⁷Lu-PSMA-617 in relation to first dose of pembrolizumab (N = 6 evaluable patients per schedule):

Schedule 1) Priming dose of ¹⁷⁷Lu-PSMA-617 administered on Cycle 1 Day 1 followed by pembrolizumab 200 mg IV q 21 days starting Cycle 2 Day 1.

Schedule 2) Priming dose of ¹⁷⁷Lu-PSMA-617 administered concurrently with initiation of pembrolizumab on Cycle 1 Day 1.

Schedule 3) Priming dose of ¹⁷⁷Lu-PSMA-617 administered on Cycle 1 Day 1 following initiation of pembrolizumab on Cycle 1 Day -21.

The priming dose of ¹⁷⁷Lu-PSMA-617 will be 7.4 +/- 15% GBq, which is the recommended phase 3 dose of the agent. If the DLT frequency exceeds 33% including patients across the three schedules, Dose Level -1 of ¹⁷⁷Lu-PSMA-617 will be investigated (4 Gbq +/- 15%).

6 evaluable patients will be enrolled in each of the three cohorts in sequential fashion in Part A of the study. The DLT window will be Cycle 1 + Cycle 2. If the DLT frequency is \geq 33% for a

particular cohort, that dosing schedule will be determined to be non-tolerable and the next schedule will be evaluated. In addition, if the DLT frequency attributable specifically to Lu-PSMA-617 is $\geq 33\%$ after 6 or more evaluable patients are enrolled in Part A of the study, the dose of Lu-PSMA-617 will be reduced to Dose Level -1 (4 GBq +/- 15%) for the remainder of patients enrolled on study. If the DLT frequency attributable to Lu-PSMA-617 at Dose Level -1 is $\geq 33\%$ after 6 or more patients are treated at Dose Level -1, study accrual will be halted.

Using the data obtained in Part A, the recommended phase 2 dose and schedule of ^{177}Lu -PSMA-617 will be determined by the DSMC and Principal Investigator using a combination of safety, efficacy, and immunologic effects of treatment from the first two cycles (and additional cycles of treatment when available).

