8.4.2 Analytic Plan for Secondary Endpoints

Median duration of response

Median duration of response will be estimated using Kaplan-Meier product limit method, starting with the date of first scan indicating response until loss of response or progression, or death, whichever occurs first.

PSA response rate

The proportion of patients who achieve a greater than 50% decline from baseline PSA drawn on C1D1, at any point in the treatment course, will be descriptively reported along with 95% confidence interval.

PSA progression free survival

PSA progression will be defined using PCWG3 criteria. Median PSA progression free survival will be estimated using the Kaplan-Meier method. Duration will be measured from date of first treatment to date of first PSA meeting criteria for PSA progression.

Time to symptomatic skeletal related event

Symptomatic skeletal related event is defined as the first occurrence of one or more of the following: symptomatic fracture, surgery or radiation to bone, or spinal cord compression. The median time to symptomatic skeletal related event will be determined using Kaplan-Meier method.

Safety

The incidence and severity of adverse events related to study treatment will be descriptively reported using CTCAE v4.0.

Radiographic progression free survival and 6-month rPFS rate:

Radiographic progression of disease will be defined by RECIST v1.1 and PCWG3 criteria. For the first scheduled reassessment by bone scan (at Cycle 2), new bone lesions will require a confirmatory bone scan 6 or more weeks later. Median PFS will be estimated using the Kaplan-Meier method. Durations will be measured from the first day of study treatment (Cycle 1) to the first date of radiographic progression or death, whichever occurs first. Patients who discontinue study treatment for toxicity, withdraw from the study, or have PSA-only progression will be censored at the date of the last radiographic tumor assessment. Patients who discontinue treatment for clinical progression or deterioration will be included in the analysis.

Overall survival

Median overall survival and 95% confidence interval will be estimated using the Kaplan-Meier method. Duration will be measured from first date of study therapy to date of death from any cause.

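### The exploratory immune-marker analyses relate percent change to outcome only through a median split, which discards information that a continuous or rank-based analysis would keep

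*Combined protocol and SAP*

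**What the plan says.** Section 8.4.3 first summarises percent change from baseline in T cell repertoire, circulating T cell subsets, tumour-infiltrating lymphocytes and PD-L1 (median, range, standard deviation). Then, "In an exploratory fashion", it says that "the study cohort will be dichotomized by those with percent change from baseline above and below median and efficacy outcomes will be compared" between the two halves. Time-to-event outcomes (rPFS and duration of response are the examples) get a log-rank test. Categorical outcomes (objective response, 6-month rPFS, PSA50) get Fisher's exact test. For PET uptake and SPECT/CT dosimetry, the same section uses Mann-Whitney and Spearman methods.

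The timing comes from other sections:

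- **rPFS origin (8.4.2):** "Durations will be measured from the first day of study treatment (Cycle 1) to the first date of radiographic progression or death".
- **Duration-of-response origin (8.4.2):** "starting with the date of first scan indicating response until loss of response or progression, or death".
- **Second biopsy (calendars 5.2 to 5.4):** "within 7 days preceding C2D1 visit" in Schedules 1 and 2; in the 14 days before C3D1 in Schedule 3.
- **Post-priming blood (calendars):** C2D1, C3D1, then every three cycles, in all schedules.
- **Schedule 3 (3.1):** the radioligand is given "following initiation of pembrolizumab on Cycle 1 Day -21".

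The plan does not say which post-dose blood draw defines the change, how many patients are expected to have paired samples, or how patients without a second sample are handled.

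**The concern.** Percent change is a continuous measure. A cut at the sample median treats a patient just above it the same as the patient with the largest increase, and treats two patients on either side of it as different. The cut-point also depends on who happens to be enrolled, so it gives no fixed threshold to carry into the randomized study that the rationale anticipates.

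This matters here because section 1.7.1 gives paired tumour biopsies, and their possible use in identifying likely responders, as one reason for raising Part B from 12 to 25 patients. Each pair costs a patient a second biopsy. With at most 43 patients, an analysis that wastes part of the signal may miss a relationship worth following up.

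**Working it through.** **1. The plan's own figure.** No power is stated for this analysis. The only power figure is for the Part B response rate (8.1: 25 patients, 10% versus 40%, two-sided 0.05, 93%). Exact binomial: at least 7 of 25 responses has upper-tail probability 0.0095 under 10% and power 0.926 under 40%; at least 6 of 25 has 0.033, above 0.025. The 93% is reproduced, but it does not bear on this point.

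**2. Information kept by a median split.** For a small linear effect, the share kept is the squared correlation between the marker and its above-median indicator. With half the patients on each side this is

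share kept = (mean above − mean below)² / (4 × variance).

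- Normal: the means differ by 2√(2/π) SD, so the share is (8/π)/4 = 2/π = 0.637.
- Uniform or rank-scored on 0 to 1: the means differ by 0.5 and the variance is 1/12, so the share is 0.25/(4/12) = 0.75.
- Exponential: the means differ by 2 ln 2 = 1.386 and the variance is 1, so the share is 1.922/4 = 0.48.

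| Assumed marker shape | Information lost |
|---|---|
| Uniform or rank-scored | 25% |
| Normal | 36% |
| Heavy-tailed (t5, Laplace) | 46%, 50% |
| Moderately skewed (lognormal s = 0.5, exponential) | 48%, 52% |
| Strongly skewed (lognormal s = 1) | 73% |

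The skewed rows assume an effect linear in the raw value. If the effect of a lognormal marker is linear on its log, the normal row applies. Right skew is plausible, because a percent change cannot fall below −100% but has no upper limit.

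**3. Power.** This is a simulation of 6,000 runs per setting, assuming a normal marker, log-linear hazard, about 20% censoring, and a pair for every patient. It compares a Cox score test on the continuous marker with a log-rank test on the split.

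| Patients (events) | True effect | Continuous | Split |
|---|---|---|---|
| 43 (about 34) | HR 1.5 per SD | 59% | 41% |
| 43 (about 34) | HR 2.0 per SD | 93% | 78% |
| 25 (about 20) | HR 1.5 per SD | 37% | 27% |
| 25 (about 20) | HR 2.0 per SD | 74% | 54% |
| 43 (about 36) | Step at the median, HR 2 | 35% | 53% |

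With no effect, rejection rates were 5.9% and 5.6% (n = 43), and 6.3% and 6.7% (n = 25), for continuous and split respectively. The gap is therefore not caused by unequal test size.

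**4. Does the rPFS clock matter?** With 21-day cycles, C2D1 is day 22, C3D1 day 43 and C4D1 day 64, counted from C1D1. The second biopsy falls on about days 15 to 22 (Schedules 1 and 2) or 29 to 43 (Schedule 3). The calendars place the first scan at C4D1 or up to 14 days earlier, about days 50 to 64, after the second biopsy and the first post-priming blood draw in every schedule.

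- In 2,000 simulated trials with a common day-22 landmark, moving the clock to the landmark changed the log-rank z by exactly 0.
- With unequal marker times (day 22; day 64 from C1D-21 in Schedule 3), the mean absolute change in z against a left-truncated log-rank test was 0.05 with 6 of 43 patients on Schedule 3, and 0.07 with 31 of 43. Type I error was 5.3% to 6.0% for both methods.

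**The case against.** The best defence is that the analysis is labelled exploratory, carries no alpha or decision rule, and fixes its cut in advance, so nobody can search for a favourable one. The percent changes are also summarised descriptively. A Cox slope with few events can be driven by one extreme value. Duration of response includes responders only, about 0.40 × 25 = 10 patients in Part B even at the design alternative. If the biology is a threshold near the median, the split is the better test.

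Most of this stands as a limit on importance. It does not justify having the split as the only analysis. Rank scaling deals with extreme values, a pre-specified continuous analysis avoids cut-point searching equally well, and the documents give no reason to expect a step at the median.

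A reader might go further and infer that, because rPFS starts before the marker is measured, the log-rank comparison is biased by guaranteed event-free time. The documents do not support that. Only patients with a second sample can be classified, so the lead is shared by both groups, and step 4 shows that the test barely moves. Duration of response already starts at the first responding scan. What remains is selection of patients who reach the second sample, and Kaplan-Meier estimates conditional on reaching it. This would matter more if a later blood draw defined the change. Section 8.4.2 also refers to a first bone scan at Cycle 2, whereas the calendars say C4D1 and section 7.6 says 9 weeks; these passages must be reconciled.

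**Conclusion.** The concern holds as an efficiency point about an exploratory analysis. The median split discards about 36% of the information for a normal marker with a linear effect, with a range from about 25% (uniform or rank-scored) to about half or more (skewed, effect linear on the raw scale). In the simulated log-linear settings, this costs 10 to 20 percentage points of power. All these sizes rest on assumed marker shapes and effects, and the ordering reverses for a true step at the median.

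A reader might also multiply the share kept by 43 or 25 and quote an effective sample size. That is not supported: the number of patients with paired samples is not given, so 43 is only an upper bound, and duration of response is confined to responders. No primary or secondary conclusion depends on this analysis.

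**What to change.** In section 8.4.3:

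- Make the main exploratory analysis continuous or rank-based. Use Cox regression on percent change (log or rank scale if skewed) for rPFS and duration of response, and Mann-Whitney or logistic regression for objective response and PSA50. Keep the median-split curves for display.
- Name the post-dose sample that defines the change for each marker and schedule.
- Report how many patients have paired samples, and how many had an event before the defining sample.
- Leave the duration-of-response origin at the first responding scan. State the rPFS origin for Schedule 3, where treatment starts at C1D-21. An rPFS landmark at the defining sample is optional; it would make Kaplan-Meier estimates easier to interpret across schedules, and is not needed to correct the test.

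This is a cheap improvement: plan wording and standard software, with no added patients, visits or samples. The downside is that the Cox slope assumes a roughly log-linear effect and loses power if the truth is a threshold at the median.
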